The PRESTIS Trial (Prospective Evaluation of Self-Testing to Increase Screening) described here is a parallel, single-blinded, three-arm RCT comparing the effectiveness of three outreach strategies for improving cervical cancer screening participation and attendance for clinical follow-up among women age 30-65 years who are overdue for Pap test screening. Being overdue for a Pap test is defined as not having a Pap test in the past 3.5 years or more, which is based on a three-year screening interval and a 6-month grace period. The study arms are: 1) telephone recall (control arm); 2) telephone recall with mailed self-sample HPV testing kit (intervention arm); and (3) telephone recall with mailed self-sample HPV testing kit and patient navigation (intervention plus arm). The primary outcome is completion of primary screening, defined as completion and return of mailed self-sample kit or completion of a clinic-based Pap test. Secondary outcomes are predictors of screening and attendance for clinical follow-up among women with a positive screening test. Additional exploratory outcomes are detection and treatment of cervical precancers and cost-effectiveness. The contribution of the PRESTIS Trial is significant because it will define how and under what conditions self-sample HPV testing can be used cost-effectively by safety net health systems for primary screening and early detection of cervical precancer among non-attendees.

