2 OBJECTIVES

2.1 Primary Objectives

The overall purpose of this protocol is to evaluate the effectiveness of self-sample HPV testing with patient navigation to increase cervical cancer screening among women who otherwise do not regularly attend for clinic-based screening (i.e., Pap test).

The specific aims of this protocol are to: SPECIFIC AIM 1: Compare the effectiveness of mailed self-sample HPV testing alone and in combination with patient navigation to increase primary screening participation (primary outcome) and clinical follow-up (secondary outcome).

Hypothesis 1.1: Primary screening participation and clinical follow-up will be significantly greater among women randomized to receive telephone recall with mailed self-sampling kits versus telephone recall alone. Hypothesis 1.2: There will be significant incremental gains in screening participation and clinical follow-up among women randomized to receive mailed self-sampling kits in combination with patient navigation.

After receiving an administrative supplement, we have revised the trial to include Asian/Asian American women who are currently under-presented in the trial and in the broader literature on self-sampling. In doing so, we will ensure that the trial is powered to rigorously assess and compare screening participation and other outcomes across racial/ethnic and linguistic subpopulations inclusive of Asian/Asian American women. Collectively, the data generated in pursuit of these aims and those of the larger trial will define the impact of mailed self-sample HPV testing among medically underserved Asian/Asian American and other racial/ethnic minority women in safety net health system settings.

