2.2 Secondary Objectives

Analytical sub-aims of the protocol are to: 1) Describe characteristics of women who under-attend for cervical cancer screening in a safety net health system; 2) Explore patterns of detection and treatment of cervical pre-cancers across study arms; 3) Compare characteristics of screening participants across study arms.

We will also conduct a nested study within the randomized controlled trial to assess acceptability of and experiences with self-sample HPV testing among underscreened women in our safety net health system. The nested study has two components: a telephone survey and in-depth

qualitative interviews. In the remainder of the protocol these will be referred to as "Telephone Survey" and "Qualitative Interviews."

Because of the COVID-19 pandemic, we have revised some elements of the trial, as reflected throughout the protocol. One of these revisions includes expansion of analytic sub-aim 1 (above) to include monitoring of ambulatory, and more specifically, primary care utilization in addition to cervical cancer screening. The COVID-19 era sub-aims are: 1) To compare changes in cervical cancer screening and primary care utilization (overall and by face-to-face vs. telehealth modalities) among socioeconomic, racial/ethnic, and nativity subgroups in the 12-months following the COVID-19 emergency declaration; and 2) To compare the role of individual and neighborhood-level factors on cervical cancer screening and primary care utilization (overall and modality-specific) before and after the COVID-19 emergency declaration. In the remainder to the protocol, we will refer to COVID-19 era analytic sub-aims.

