3.4 Data Analysis

Randomized Controlled Trial Primary outcome. Primary screening participation will be examined dichotomously (screened/not screened) using an "intent-to-screen" analytic approach. Bivariable tables and Pearson's χ^2 tests will be used to compare the proportion of primary screening participation across Arms 1, 2, and 3, as well as the absolute difference in participation across Arms 1, 2 and 3. Bivariable tables and Pearson's χ^2 tests will be used to compare the proportion of primary screening participation by study arm, as well as the absolute difference in participation across arms. Log binomial regression will be used to calculate the relative risks of primary screening participation and corresponding 95% confidence intervals (CIs). Secondary outcomes. Descriptive analyses of secondary outcomes will be conducted using bivariable tables and Fisher's exact tests to describe and compare test results and attendance for clinical follow-up across study arms 1, 2 and 3. Log binomial regression will be used to calculate relative risks and 95% CIs of having a positive screening test and of attending for clinical follow-up.

Analytic sub-aim: 1) We will use descriptive statistics (bivariable tables and chi-square/Fisher's exact tests) to compare characteristics of un/under-screened women and those who are up-to-date on screening across Arms 1, 2, and 3. Multivariable logistic regression will be used to assess the independent association between screening status and participant characteristics. 2) Detection and treatment of precancers will be explored through descriptive analyses using bivariable tables and Fisher's exact tests. 3) Among participants in Arms 1, 2 and 3, we will conduct separate analyses to assess characteristics associated with primary screening participation. For Arms 1, 2 and 3, we will use bivariable tables with Pearson's χ^2 tests to describe characteristics of screened and unscreened participants. Characteristics of interest include age, race/ethnicity, months since last Pap test, health plan type, number of healthcare encounters in the past 12 months, and time enrolled as a Harris Health patient. Associations with $p<0.10$ will be used to determine candidate variables for subsequent multivariable

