models. Multivariable log binomial regression models will be built to assess the independent association between screening participation and participant characteristics after adjusting for relevant covariates. The likelihood ratio test will be used to examine the relative contribution of specific variables to the fit of the model. Adjusted risk ratios will be reported and will be considered statistically significant at $p<0.05$.

Telephone Survey Descriptive statistics will be used to identify experiences of self-sampling among survey participants who completed and returned a kit. The main effects of patient navigation on overall experience will be assessed using bivariable tables and Pearson's χ^2 or Fisher's exact tests. Associations with $p<0.05$ will be considered statistically significant. Additionally, we will explore patterns related to specific barriers in the scale using exploratory bivariable analyses. For those participants who did not return a kit, descriptive statistics will be used to describe barriers to clinic-based screening and reasons for using the self-sampling kit. Bivariable tables and Pearson's χ^2 or Fisher's exact tests will be used to explore differences in barriers to clinic-based screening between kit returners and non-returners.

Qualitative Interviews The semi-structured interviews will be transcribed by a professional transcription service and kept in the language in which they were conducted (English or Spanish). The PI, who is bilingual in English and Spanish and experienced in qualitative data analysis, will conduct a close reading of the transcripts to develop a coding scheme. Once the coding scheme is developed, coding rules and procedures will be detailed in a codebook and described to two independent coders (the research coordinator and research assistant) who will classify the dataset. Cohen's Kappa coefficient [86] will be used to evaluate inter-coder reliability. Iterative content analysis will be used to collapse codes into emergent themes. A summative approach will be used to describe and compare codes and themes across women who do and do not attend for clinical follow-up.

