COVID-19 era analytic sub-aim: 1) We will use descriptive statistics (bivariable tables and chi-square/Fisher's exact tests) to compare characteristics of women who do/do not attend for cervical cancer screening, primary care (all types), and telehealth-specific primary care. We will compare proportions at baseline (February 2020, pre-pandemic), and at 6- and 12-months post COVID-19 emergency declaration (July 2020 and February 2021). Independent multivariable Poisson regression models will be used to assess the independent association between cervical cancer screening and primary care utilization and participant characteristics.

Additional variables will be collected to meet the aims of the NIH-funded supplement (3R01MD013715-04S1) to the parent self-sampling trial: HIV status, Preventive Care Gap Score, Enrollment in MyHealth portal, History of COVID-19 diagnosis, HPV vaccination status and Risk of Admission or ED visit.

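### Sub-aim 3 promises a comparison of screened women's characteristics across arms, but Section 3.4 gives no between-arm contrast and picks model covariates by a bivariable p<0.10 filter

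*Combined protocol and SAP*

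**What the plan says.** Section 2.2 words sub-aim 3 as "Compare characteristics of screening participants across study arms". Section 3.4 gives its analysis in four steps.

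- For Arms 1, 2 and 3, "we will conduct separate analyses to assess characteristics associated with primary screening participation", starting with bivariable tables and Pearson tests of screened against unscreened women.
- The variables are introduced by "Characteristics of interest include age, race/ethnicity, months since last Pap test, health plan type, number of healthcare encounters in the past 12 months"; time as a Harris Health patient is the sixth.
- Associations at p<0.10 "will be used to determine candidate variables for subsequent multivariable" models.
- Log binomial models are then fitted "to assess the independent association between screening participation and participant characteristics after adjusting for relevant covariates". Likelihood ratio tests judge what single variables add to the fit, and adjusted RRs are called significant at p<0.05.

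The relevant covariates are not defined, and no rule leads from the candidates to the final model, so p<0.10 is the only numeric selection rule stated.

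**The concern.** There are two separate gaps.

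First, the objective is a contrast between arms, while every analysis listed for it is a contrast between screened and unscreened women. The plan would show who gets screened. It would give no estimate, interval or test of whether that differs between recall alone, a mailed kit, and a kit with navigation. Whether a kit reaches different women from a telephone recall is the question that sub-aim 3 raises.

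Second, the data decide which characteristics receive an adjusted RR. A weak association passes p<0.10 mainly when chance has exaggerated it, so the adjusted RRs that are published for weak associations tend to be too large and their intervals cover too seldom. If the filter is applied within each arm, the arms can also be adjusted for different covariates, and their adjusted RRs then no longer estimate the same thing.

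**Working it through.** **Text check.** The documents give no sample size, power or event figure for sub-aim 3, so there is no plan figure to reproduce. Section 3.4 does state between-arm comparisons for the primary outcome and for the secondary outcomes (test results, attendance for follow-up). Under sub-aim 1 the arms are mentioned, but the contrast there is under-screened against up-to-date women. Under sub-aim 3 no arm term, arm-by-characteristic term or heterogeneity test appears, and screened women in one arm are not compared with screened women in another. The likelihood ratio test is not described as a test of interaction with arm. *Separate* most naturally means one analysis per arm, but no reading supplies the contrast.

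**Inputs for the illustrations.** 756 women per arm and 2,268 in total (Section 4). Assumed, because the documents give no Arm 1 rate: participation of 15/20/26% in Arms 1/2/3 (the last step matches the 6-point planning difference in Section 4), and a binary characteristic split 50:50, so 378 v 378 within an arm. With arm rate p, the two groups have rates 2p/(1+RR) and RR x 2p/(1+RR).

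**Filter.** Simulation of 400,000 runs with one characteristic, kept if p<0.10. The second-stage estimate is taken as the bivariable RR, which treats the characteristics as independent.

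| | Arm 1 | Arm 2 | Arm 3 | Pooled |
|---|---|---|---|---|
| P(pass), true RR 1.2 | 0.28 | 0.35 | 0.44 | 0.71 |
| P(pass), true RR 1.3 | 0.45 | 0.56 | 0.69 | 0.93 |
| Mean RR if passed, true 1.1 | 1.36 | 1.32 | 1.29 | 1.21 |
| Mean RR if passed, true 1.3 | 1.52 | 1.44 | 1.39 | 1.32 |
| CI coverage if passed, true 1.1 | 0.75 | 0.80 | 0.84 | 0.91 |
| CI coverage if passed, true 1.3 | 0.95 | 0.96 | 0.97 | 0.97 |

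The means are averaged on the log scale. Arithmetic means for a true RR of 1.1 within arm are 1.39/1.34/1.29, hence about 1.3-1.4.

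**Different covariate sets, only if selection is within arm.** For one null characteristic, the chance that the three arms do not all agree is 1 - 0.9^3 - 0.1^3 = 0.27. For at least one of six it is 1 - 0.73^6 = 0.85.

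**Why per-arm results cannot stand in for the contrast.** Let the true RR be 1.3 in every arm. The group rates are 13.0% v 17.0%, 17.4% v 22.6% and 22.6% v 29.4%, and two-sided 5% power is 0.325, 0.434 and 0.566. The chance that the arms disagree on significance is 1 - (0.325 x 0.434 x 0.566) - (0.675 x 0.566 x 0.434) = 1 - 0.080 - 0.166 = 0.75. The same sum gives 0.28 at RR 1.1, 0.54 at 1.5 and 0.03 at 2.0. With Arm 1 at 10, 15 or 20% and the 12.8- and 6-point differences of Section 4 added in turn, the RR 1.3 figure is 0.72-0.78.

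**Precision of the missing contrast.** With no association, the variance of log RR within an arm is 2(1-p)/(378p): 0.0300, 0.0212 and 0.0151 at 15, 20 and 26%. The SE of the log ratio of RRs is the root of the sum of two of these: 0.226 (Arms 1 v 2), 0.212 (1 v 3) and 0.190 (2 v 3). The detectable ratio at 80% power is exp(2.80 x SE) = 1.88, 1.81 and 1.70. Over all the assumed rate sets the range is about 1.5-2.2. Power for a true ratio of 1.25 is 17-22%.

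**The case against.** The best defence is that sub-aim 3 is descriptive. The bivariable tables cover every characteristic of interest, and arm-by-arm tables let a reader compare. This stands in part: a characteristic that fails the filter loses its adjusted RR, not its unadjusted comparison. But tables of screened against unscreened women give no estimate or interval for a difference between arms.

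Four stronger readings are tempting, and the documents do not support them.

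- A reader might infer that arm differences will be read off lists of significant predictors. The plan does not say so. The 75% disagreement rate describes a hazard, not a planned step, and the filter does not cause it.
- A reader might infer that the filter makes every reported interval too optimistic. It does not: coverage is 95-97% at RR 1.3. For a null characteristic, coverage among those that pass is about 51%, but that is close to 1 - 0.05/0.10 and applies only to the 10% that pass. The unconditional false-positive rate stays at about 5%.
- A reader might infer that the filter can undo the Section 2.1 statement that the trial is "powered to rigorously assess and compare screening participation and other outcomes across racial/ethnic and linguistic subpopulations". That statement belongs to the supplement and is not tied to sub-aim 3. The list in Section 3.4 is also open, so the absence of language from it proves little. Whether that comparison has an analysis of its own is a separate matter.
- A reader might infer that the primary result is compromised. The crude primary contrast between arms is valid and does not use these models.

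It is also fair to say that the replacement analysis has low power. That is a reason to label it exploratory, not to leave the contrast unstated.

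**Conclusion.** The mismatch between Section 2.2 and Section 3.4 is plain from the text and rests on no assumption. The filter is a second, independent weakness that matters for weak associations: selected point estimates are inflated, and coverage falls short near RR 1.1 but not at RR 1.3. Its size depends on the assumed rates, the 50:50 split and independent characteristics, and the planned multivariable step itself was not simulated.

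Severity is minor. The primary conclusion is untouched, and sub-aim 3 is an analytical sub-aim. Section 1.2 says "Secondary outcomes are predictors of screening and attendance for clinical follow-up among women with a positive screening test", but the outcome definitions in Sections 3.1 and 6.1 do not list predictors of screening among the secondary outcomes.

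**What to change.** In Section 3.4, for sub-aim 3:

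- Drop the p<0.10 filter. Use the six listed characteristics, with categories fixed in advance, in one common model over all arms.
- Estimate arm-by-characteristic ratios of RRs with 95% CIs, one characteristic at a time, with the others as main effects. This addresses the sub-aim directly. If baseline prevalence is equal between arms, as randomisation gives in expectation, the odds of a characteristic among screened women equal its baseline odds times that arm's RR. The ratio of those odds between two arms is then the ratio of RRs.
- Report all of them, labelled exploratory, and do not infer arm differences from side-by-side p-values.
- If the log binomial model does not converge, use modified Poisson with robust errors. Section 3.4 already says for the COVID-19 era sub-aim that "Independent multivariable Poisson regression models will be used".

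The cost is SAP wording and modest analysis work, with no new data. The price is imprecise estimates, as shown above. Multi-level characteristics such as race/ethnicity may need collapsing in advance: at an assumed 10% in Arm 1 there are only about 76 events (756 x 0.10).

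A primary contrast adjusted for the same baseline characteristics, beside the crude one, is an optional addition and not part of this defect.

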2.3 Study Type

We expect higher participation in cervical screening among those participants who receive the self-collection kit with additional patient navigation.

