4 STUDY POPULATION

Randomized Controlled Trial In a systematic review, patient navigation was associated with a 15% improvement over standard of care for completion of primary colorectal cancer screening, with the proportion of participants who complete screening after navigation ranging from 27-67%. As the degree to which HPV and colorectal screening are analogous is unknown, we chose to err on the conservative side and, in order to ensure adequate power, based our calculations on the assumption that at least a 6% difference exists between screening non-attendees who complete mailed self-sample HPV testing with patient navigation compared to those who complete the self-sample testing without patient navigation. With 756 participants in each study arm and a total of 2,268 (nQueryAdvisor version 7.0), we can expect to detect the indicated differences in proportions between Arms 2 and 3. Given the large numbers of screening non-attendees enrolled in Harris Health (>15,000), we anticipate that we will be able to accrue this number of participants over a period of 30 months, with completion of follow-up in 36 months.

The sample size has been revised to account for an additional 240 Asian/Asian American women who will be enrolled as part of an administrative supplement. For the Asian/Asian American targeted enrollment study, the estimated number of participants who can be enrolled in a six month period with the two patient navigators who will remain on the team is 240. A recent meta-analysis of trials showed a pooled 12.8% improvement in intent-to-treat analyses measuring screening uptake in mail-to-all self-sample HPV testing

compared to usual care (4). Using this data, our sample size of 240 (120 in Arm 1, 60 each in Arms 2 and 3) provides 85.2% power to detect an improvement of 12.8% between usual care (Arm 1) and mailed self-sampling (Arms 2 and 3 combined) with alpha=0.05 (30).

Telephone Survey The sample size is designed to assess the main effect of patient navigation on reported barriers to self-sampling. Specifically, it is designed to detect a 25% difference in the proportion of participants who report one of the top three barriers reported in our previous research (concerns of injury, safety, and cleanliness), comparing women who did and did not receive patient navigation. Specifying an expected proportion of 0.30, 80% power, and $\alpha=0.05$, the target sample size is 272 (n=68 in each group of the factorial design).

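### The survey's test of navigation on self-sampling experience, on its natural reading, compares kit returners, a group the plan expects navigation to enlarge; it supports an association, not an effect

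*Combined protocol and SAP*

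**What the plan says.** The telephone survey paragraph appears in section 3.2 and again in section 3.4. It begins: "Descriptive statistics will be used to identify experiences of self-sampling among survey participants who completed and returned a kit". The next sentence reads: "The main effects of patient navigation on overall experience will be assessed using bivariable tables", using Pearson chi-square or Fisher's exact tests. Then comes the threshold: "Associations with $p<0.05$ will be considered statistically significant". Women who kept the kit are treated separately and asked about other things: "For those participants who did not return a kit, descriptive statistics will be used to describe barriers to clinic-based screening", together with reasons for using the kit.

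Elsewhere the plan expects navigation to change who returns a kit. Section 4 assumes that "at least a 6% difference exists between screening non-attendees who complete mailed self-sample HPV testing with patient navigation compared to those who complete" it without navigation. Section 2.3 adds: "We expect higher participation in cervical screening among those participants who receive the self-collection kit with additional patient navigation". Section 3.1 gives the means: in Arm 3 only, one-to-one education, instruction on using the kit, and up to three telephone reminders.

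Section 4.2 bars from the survey women who test HR-HPV positive and need follow-up. Sections 4.4 and 6.2 require verbal agreement to take part. No adjustment, estimand, sensitivity analysis or limit on interpretation is given for the navigation comparison.

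**The concern.** Randomisation makes all women in Arm 2 comparable with all women in Arm 3. It does not make the returners comparable if navigation influences who returns. If the trial's own hypothesis is right, Arm 3 returners are a mixture of women who would have returned a kit anyway and women who returned one because they were navigated. Arm 2 returners contain only the first kind. A difference in reported experience can then reflect the mixture and not anything navigation did to the experience.

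The survey text attaches the language of a main effect, and a significance threshold, to this contrast. Section 8 says the survey data may be used to improve the intervention, so a difference wrongly read as an effect could be carried forward.

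**Working it through.** **The plan's own figure.** Section 4 gives 68 per group and 272 in total, for a 25-point difference from 0.30 with 80% power and alpha 0.05. Take 0.30 versus 0.55, two-sided:

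- Uncorrected: n = [1.96 × sqrt(2 × 0.425 × 0.575) + 0.842 × sqrt(0.30 × 0.70 + 0.55 × 0.45)]² / 0.25² = 60.2, or 61.
- Continuity-corrected: (60.2/4) × [1 + sqrt(1 + 4/(60.2 × 0.25))]² = 67.95, or 68.
- 68 × 4 = 272, as stated.

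This reproduces the plan, but the endpoint is reported barriers to self-sampling. No design figure is given for overall experience.

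**Inputs for the mixture.**

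- Gain in kit return from navigation: 6 percentage points (section 4, stated as a minimum).
- Arm 2 return r2: 10% to 39% (section 1.2, trials outside the US). The plan gives no figure for its own Arm 2, so applying this range is an assumption.
- Gap g in reported experience between navigation-induced returners and other returners: not in the documents; assumed 0 to 30 points, in either direction.
- Navigation never stops a return: an assumption.

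**Formulas.** Share of Arm 3 returners who are there only because of navigation: f = 0.06 / (r2 + 0.06). Arm difference when navigation has no effect on experience: f × g.

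| r2 | f | g = 0 | g = 10 | g = 20 | g = 30 |
|---|---|---|---|---|---|
| 10% | 0.06/0.16 = 37.5% | 0 | 3.8 | 7.5 | 11.3 |
| 20% | 0.06/0.26 = 23.1% | 0 | 2.3 | 4.6 | 6.9 |
| 39% | 0.06/0.45 = 13.3% | 0 | 1.3 | 2.7 | 4.0 |

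(Differences in percentage points.)

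**What this does to the test.** Assume 68 surveyed returners per arm and a base proportion of 0.30, both borrowed from the barriers calculation. By normal approximation, the nominal 5% error rate becomes:

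- g = 10: 7.5%, 6.0% and 5.3% at r2 = 10%, 20% and 39%.
- g = 20: 15.1%, 8.8% and 6.3%.
- g = 30: 27.7%, 13.6% and 7.9%.

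A simulation of the chi-square test at r2 = 10% and 39% agreed to within about 0.7 percentage points.

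**Masking.** This needs a real effect. A true 25-point change (0.55 to 0.30) has 85% power with 68 per arm. An opposing gap of 20 points lowers that to 54% at r2 = 10%, or 75% at r2 = 39%.

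**The case against.** **The population is inferred.** This stands. The navigation sentence names none, and section 4 refers to a factorial design of four groups, in which a main effect would ordinarily mean one factor averaged over the other. The questionnaire is attached and not shown, so who answers the experience items cannot be confirmed. Returners remain the natural reading, since the preceding sentence is about them and experience of self-sampling requires having used a kit. The averaged reading does not remove the problem. If return status is the other factor, fixing the numbers of returners and non-returners still conditions on something that happens after randomisation.

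**The text already speaks of associations.** It does, in the sentence on significance. But it follows a sentence that names main effects of navigation, and the plan separates that test from its descriptive statistics.

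**The gap is unsupported.** This also stands. A reader might infer that the extra returners are more reluctant women who would rate self-sampling lower, so that Arm 3 would look worse. The documents do not say so. The gap could be zero, in which case there is no bias, or could run in either direction.

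**The stakes are limited.** A reader might also infer that the decision to add navigation would be misdirected. The documents do not tie that decision to this survey. Hypothesis 1.2 in section 2.1 concerns screening participation and clinical follow-up, and participation is analysed by intent to screen. The survey is a nested acceptability study under the secondary objectives.

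**Navigation may divert some returns.** Section 3.1 offers Arm 3 women who prefer a Pap test help with scheduling, so a few who would have returned a kit in Arm 2 may not do so in Arm 3. The simple mixture and any trimming bounds both assume this does not happen.

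**Conclusion.** The concern holds in a limited form. On the natural reading, the comparison conditions on kit return, which the plan itself expects navigation to raise, and it is described as a main effect with nothing to limit that claim.

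Under the 6-point gain, Arm 2 return of 10-39% and no discouraged returns, about 38% to 13% of Arm 3 returners are there only because of navigation. With an assumed gap of 0 to 30 points, the arms differ by 0 to 11 points without any effect on experience. The top of that range needs both the lowest return rate and the largest gap; at a 10-point gap the difference is 1 to 4 points. Partial masking is possible only where navigation has a real effect.

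The exclusion of HR-HPV positive women and the need for agreement to be surveyed are further selections after randomisation, which these figures do not include. The primary outcome analysis is untouched.

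**What to change.** In sections 3.2 and 3.4, replace the wording that begins "The main effects of patient navigation on overall experience will be assessed using bivariable tables" with: *difference in reported experience between surveyed Arm 2 and Arm 3 kit returners, reported as an association and not as an effect of navigation*. This also states the population.

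Beside the result, report for each arm, per woman randomised, the proportions who:

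- returned a kit;
- were eligible for the survey after the HR-HPV-positive exclusion in section 4.2;
- were surveyed.

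As an optional sensitivity analysis, give trimming (Lee) bounds. Base the trimmed fraction on survey-eligible returners per woman randomised, because raw return proportions ignore the section 4.2 exclusion. State the assumption that navigation never discourages return, and that selection through agreement to be surveyed remains. The bounds may be too wide to help. If 70% of Arm 3 returners report good experience (an assumption), and the trimmed fraction equals f above:

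- f = 37.5%: (0.70 − 0.375)/0.625 = 52% to 100%, 48 points wide.
- f = 23.1%: (0.70 − 0.231)/0.769 = 61% to 0.70/0.769 = 91%, 30 points wide.
- f = 13.3%: (0.70 − 0.133)/0.867 = 65% to 0.70/0.867 = 81%, about 15 points wide.

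These widths are before sampling error. The required change is wording plus a few counts, with no new data collection or sample size. Its cost is a weaker claim than a single p-value for an effect.
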